4.3.3 Investigational Medicinal Product Accountability

The IMP required for completion of this study (rituximab) will be provided by Roche. The investigational site will acknowledge receipt of IMP, using the IxRS to confirm the shipment condition and contents. Any damaged shipments will be replaced.

IMP will either be disposed of at the study site according to the study site's institutional standard operating procedure or returned to Roche with the appropriate documentation. The site's method of IMP destruction must be agreed upon by Roche. The site must obtain written authorization from Roche before any IMP is destroyed, and IMP destruction must be documented on the appropriate form.

Accurate records of all IMPs received at, dispensed from, returned to, and disposed of by the study site should be recorded on the Drug Inventory Log.

4.3.4 Retreatment with Rituximab

After Month 6, if patients require retreatment with rituximab, further courses will be provided by the Sponsor until the common closeout date. The dose of rituximab and the frequency of retreatment for the maintenance of remission will be at the discretion of the investigator.

Following administration of the first infusion the investigator should review the following safety criteria before administering subsequent infusions of rituximab.

The following are absolute contraindications to receipt of further infusions of rituximab in this study:

- An infusion reaction which necessitated complete discontinuation of the study infusions
- Significant deterioration in patient's general health status since inclusion into the study that results in the patient meeting the exclusion criteria related to General Health
- Emergent primary or secondary immunodeficiency recognized during the study period, including new HIV infection, de novo hepatitis B, hepatitis C, or active tuberculosis infection

Patients who have any of the absolute contraindications to receipt of study infusions with rituximab will be withdrawn from the study and should be encouraged to enter Follow Up.

Patients who develop malignancy during the study will not be able to receive further courses of treatment with the study medication. However, patients with basal cell carcinoma, squamous cell carcinoma of the skin or melanoma in situ (Clarke's Level I), or cervical carcinoma in situ with no stromal invasion (stage 0), which have been completely excised and can be considered as cured, may be retreated with study medication at the discretion of the investigator.

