4.5 STUDY ASSESSMENTS

The sequence of assessments at each visit will be standardized as follows (at visits required by the schedule of assessments) and should be performed prior to infusion, with the exception of the post-dose PK sample.

1. PRO assessments: [REDACTED]
2. Efficacy assessments: [REDACTED], and per schedule of assessments (see [Appendix 1](#))
3. Laboratory samples: All samples (including for safety and efficacy) must be obtained prior to study drug treatment, except for some samples for PK analysis, which will be obtained after study drug treatment. The laboratory samples can be drawn either at least 30 minutes before or at any time after the nurse or investigator assessments.
4. Safety assessments: review of AEs, vital signs, concomitant medications, and laboratory data
5. Post-dose PK sample (at scheduled visits, where indicated). The post-infusion PK sample should be taken from the opposite arm to that into which the rituximab infusion was administered.

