4.5.6.2 Baseline Assessments (Day 1) and Remission Induction Phase

Patients must receive three doses of methylprednisolone at 30 mg/kg/day (up to 1 g/day) or the equivalent dose of other glucocorticoids by IV infusion, which can occur at any time, up to and including Day 1. If clinically indicated, and at the discretion of the investigator, additional daily doses (up to three) of methylprednisolone (30 mg/kg, up to 1 g/day) can be given by IV infusion. No more than six doses in total may be given. All doses of methylprednisolone must be completed prior to the first rituximab infusion.

The first rituximab infusion (baseline visit) must occur no longer than 14 days after the final IV glucocorticoid dose; the final IV glucocorticoid dose may be given on Day 1 (prior to the first rituximab infusion).

All assessments must be performed on the day of the specified visit, unless a time window is specified in the schedule of assessments (see [Appendix 2](#)). Assessments scheduled on the day of study treatment administration should be performed prior to administration of study treatment, unless otherwise noted in the schedule of assessments. PRO assessments should be performed prior to the completion of other study assessments.

Please see [Appendix 1](#) for the schedule of assessments performed during the treatment period.

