4.5.8 Unscheduled Visits

Patients may attend the clinic for unscheduled visits at any time for additional safety monitoring or disease surveillance at the discretion of the investigator. If a patient has an unscheduled visit during the study that falls outside of a scheduled visit window, assessments will be performed at the discretion of the investigator. If a patient has an unscheduled visit within a scheduled visit window, it is at the discretion of the investigator to perform the scheduled assessments indicated for the scheduled visit.

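### After Month 6 the required urine pregnancy test follows the 3-monthly visits and not the infusion, so a retreatment infusion given off a scheduled visit has no required pre-dose test

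*Protocol*

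**What the plan says.** Retreatment (Protocol Section 4.3.4): "The dose of rituximab and the frequency of retreatment for the maintenance of remission will be at the discretion of the investigator". Before further infusions there is a review, not a test: "Following administration of the first infusion the investigator should review the following safety criteria before administering subsequent infusions of rituximab". The absolute contraindications that follow are an infusion reaction that ended the study infusions, a decline in health that brings the patient within the General Health exclusions, and new immunodeficiency or certain infections. Pregnancy is one of the General Health exclusions in Section 4.1.2, but the route to it is worded as "Significant deterioration in patient's general health status since inclusion into the study".

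Testing (Protocol Appendix 1; the limit to females of childbearing potential is footnote i in SAP Appendix 2): a urine test at baseline, Weeks 1 to 3, Months 1, 2, 4, 6, 9, 12, 15 and 18, every 3 months after that, at withdrawal and in extended follow-up. The rituximab row is marked only at baseline and Weeks 1 to 3. Neither Appendix 1 nor Appendix 2 has a retreatment visit.

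Order of events: under Section 4.5, assessments at visits in the schedule "should be performed prior to infusion, with the exception of the post-dose PK sample". Section 4.5.6.2 says the same for the induction phase: "Assessments scheduled on the day of study treatment administration should be performed prior to administration of study treatment".

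Other days (Section 4.5.8): if an unscheduled visit "falls outside of a scheduled visit window, assessments will be performed at the discretion of the investigator". If it falls "within a scheduled visit window, it is at the discretion of the investigator to perform the scheduled assessments".

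Other pregnancy provisions: contraception is an entry requirement (Section 4.1.1) and is advised for up to 12 months after treatment (Section 5.2.3.9). The test-based exclusion in Section 4.1.2 concerns screening and the first infusion. Section 5.2.3.9 advises against dosing in pregnancy unless benefit outweighs risk. Section 5.4.3.1 stops study drug once a pregnancy is known.

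**The concern.** In induction, test and infusion share a visit. After Month 6 the test stays on the calendar while the infusion moves to whatever day the investigator chooses. Rituximab is a listed option for major relapse in Section 4.4.2.1, and relapses do not wait for a 3-monthly visit. Any course of several infusions also puts most of them between visits.

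With the protocol followed exactly, an adolescent whose contraception has failed and whose pregnancy is not yet recognised could receive sponsor-supplied rituximab. The stop in Section 5.4.3.1 would then come after the dose. Section 5.2.3.9 says why this matters: IgG crosses the placenta, and B-cell depletion and low lymphocyte counts, described as transient, have been reported in some exposed infants. The protocol does attach a check to retreatment elsewhere: Section 4.4.3.2 recommends reviewing vaccination needs before a further course. Pregnancy testing has no equivalent.

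**Working it through.** The plan states no figure on this point, so there is none to reproduce. The check has three steps.

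**1. Is a test required on the infusion day?**

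| Infusion | Required test? | Source |
|---|---|---|
| Induction, Days 1, 8, 15, 22 | Yes, at each visit | Appendix 1 (footnote c lets the investigator accept baseline assessments done within 14 days) |
| Retreatment at a scheduled visit | Yes, before dosing | Appendix 1, Section 4.5 |
| Retreatment at an unscheduled visit, inside or outside a window | No, discretionary | Section 4.5.8 |

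Nothing else supplies the missing requirement. Section 4.3.4 asks for no test, Sections 5.2.3.9 and 5.4.3.1 act on a known pregnancy, Appendix 7 covers infusion procedures without a test, and SAP Appendix 2 repeats the same schedule.

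**2. How old can the last required test be?** Inputs are the Protocol Appendix 2 target days and windows: Month 6, 180 ± 5; Month 9, 270 ± 10; Month 12, 365 ± 10; Month 15, 455 ± 10; Month 18, 545 ± 10. For an infusion outside every window:

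- latest infusion day = next target − 10 − 1
- test age, previous visit on target = latest infusion day − previous target
- test age, previous visit as early as allowed = latest infusion day − (previous target − its window)

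| Interval | Latest infusion day | Previous visit on target | Previous visit earliest |
|---|---|---|---|
| Month 6 to 9 | 270 − 11 = 259 | 259 − 180 = 79 | 259 − 175 = 84 |
| Month 9 to 12 | 365 − 11 = 354 | 354 − 270 = 84 | 354 − 260 = 94 |
| Month 12 to 15 | 455 − 11 = 444 | 444 − 365 = 79 | 444 − 355 = 89 |
| Month 15 to 18 | 545 − 11 = 534 | 534 − 455 = 79 | 534 − 445 = 89 |

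The maximum is thus 79 to 84 days on the nominal calendar and 84 to 94 days with an early previous visit. Infusions earlier in an interval follow the last test more closely.

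**3. What share of infusions has no required same-day test?** The retreatment regimen is not fixed, so this rests on assumed regimens. The shortest distances between consecutive scheduled visits are:

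- (270 − 10) − (180 + 5) = 75
- (365 − 10) − (270 + 10) = 75
- (455 − 10) − (365 + 10) = 70
- (545 − 10) − (455 + 10) = 70

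A four-weekly course spans 3 × 7 = 21 days, less than 70, so at most one infusion can fall on a scheduled visit.

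- Four weekly infusions: 3 of 4 untested on the day if one falls on a visit, otherwise 4 of 4.
- Two infusions 14 days apart: 1 of 2 or 2 of 2.
- Single infusion: 0 or 1 of 1, which is the whole possible range and so uninformative.

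If a four-weekly course starts at a scheduled visit, the three later infusions come 7, 14 and 21 days after a required test. The count is then high but the delay short.

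**The case against.** Several controls already apply. Contraception is required, testing recurs every 3 months, investigators may test at any visit, and the Section 4.3.4 review points to exclusions that include pregnancy. Harm needs a conjunction: childbearing potential, retreatment, an off-visit infusion, contraceptive failure, an unrecognised pregnancy and an investigator who does not test. The study plans for at least 25 patients aged 2 to under 18. Section 5.2.3.9 also reports no embryotoxicity in monkeys. SAP output AE002.2SP lists infusion reactions at Months 6, 12 and 18, all scheduled visits, which suggests that retreatment may have been expected there. All of this limits the likely number of cases. None of it requires a test, and an output's visit list does not fix when infusions are given.

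A reader might infer more than the documents support:

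- *That no retreatment infusion is preceded by a required test.* Infusions at scheduled visits are covered by Section 4.5 and Appendix 1.
- *That the last test could be 104 to 114 days old.* The longest window-to-window intervals are 105 to 115 days, so an infusion one day before the next visit gives those figures. But that day lies inside the next visit's window and could be run as that visit. Section 4.5.8 permits the sequence, but it is contrived.
- *That two four-weekly courses starting at Months 12 and 18 leave 6 of 8 infusions effectively untested.* Those six come only 7 to 21 days after a required test.

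**Conclusion.** The gap is real and no other text closes it: a retreatment infusion off a scheduled visit has no required pre-dose pregnancy test. For infusions outside every window between Months 6 and 18, the last required test can be up to 79 to 84 days old nominally, or 84 to 94 days after an early previous visit. These figures assume that visits keep to Appendix 2. The figure of at least 3 of 4 infusions without a same-day test also assumes a four-weekly retreatment course.

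The documents give neither the number of girls of childbearing potential nor the number retreated, so the number affected is unknown; it is probably small. The existing controls lower the risk but do not detect a pregnancy before an off-visit dose. The change should be made because it protects patients at very little cost. The point does not call any planned analysis into question.

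**What to change.** Add to Section 4.3.4 and as an Appendix 1 footnote: *For females of childbearing potential, a urine pregnancy test must be negative before each retreatment infusion, whether or not the infusion falls on a scheduled visit.* At minimum, require it before each course. That removes the long interval but leaves later infusions of a four-weekly course 7 to 21 days after the test.

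A positive dipstick should be confirmed, and a confirmed pregnancy handled under the existing Sections 5.2.3.9 and 5.4.3.1. Two further changes should be avoided:

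- Do not add pregnancy to the Section 4.3.4 contraindications, because of their consequence: "Patients who have any of the absolute contraindications to receipt of study infusions with rituximab will be withdrawn from the study". Section 5.4.3.1 wants monitoring to continue until the pregnancy ends.
- Do not make a positive test an automatic withdrawal from study treatment under Section 3.1.8. That would turn an unconfirmed dipstick into a permanent bar on study rituximab, remove the benefit-risk judgement in Section 5.2.3.9, and might conflict with the General Health item in Section 4.3.4.

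The cost is one extra urine dipstick per off-visit infusion, already a local test under Section 4.5.3.5, and an occasional delay while a positive result is confirmed.

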3.1.8 Early Study Drug Withdrawal

The investigator may also withdraw a participant from study treatment if he or she judges that continuing on rituximab is no longer in the participant's best interest. These participants will remain in the study *for follow-up*, but will be asked to complete a withdrawal visit (see [Appendix 1](#)). *From the point of withdrawal, a patient may no longer receive rituximab as part of this protocol.* They will continue to be followed until the common closeout date. At the common closeout date, patients whose *peripheral B* cells remain depleted, will continue to attend study visits every 3 months until their

peripheral B-cell counts have returned to *pre-rituximab* baseline level or to within the normal range for the population, whichever is lower (see Section 3.1.4).

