4.5.7 Early Withdrawal Visit

Patients who discontinue from the study early because of non-compliance or withdrawal of consent will be asked to return to the clinic to attend an early withdrawal visit and will be encouraged to enter follow up.

If the investigator judges that continuing rituximab is no longer in the participant's best interest, the participant will be asked to complete a withdrawal visit and will remain in the study *for follow-up (see Section 3.1.8)*. *From the point of withdrawal, a patient may no longer receive rituximab as part of this protocol*. A schedule of assessments for the withdrawal visit is provided in [Appendix 1](#).

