All patients who permanently discontinue infusions of rituximab but have not terminated study participation (withdrawn consent or have been withdrawn by the investigator or Sponsor according to the above examples) will have safety evaluations, including all withdrawal visits, as shown in the schedule of assessments (see [Appendix 1](#)). If the reason for withdrawal of a patient from the study drug is an AE, the principal specific event will be recorded on the eCRF. If possible, the patient should not be withdrawn from the study but only from study drug and, if possible, should be followed until the AE has resolved (see Section [5.5.1](#)). An excessive rate of withdrawals can render the study non-interpretable; therefore, unnecessary withdrawal of patients should be avoided. Should a patient decide to withdraw, all efforts will be made to complete and report the observations prior to withdrawal as thoroughly as possible.

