Anaphylactic and other hypersensitivity reactions have been reported following the IV administration of proteins to patients. Medicinal products for the treatment of hypersensitivity reactions (e.g., epinephrine, antihistamines, and glucocorticoids) must be available for immediate use in the event of an allergic reaction during administration of rituximab. If a patient has symptoms of anaphylaxis or serious hypersensitivity, or

requires an interruption of the study drug because of symptoms of anaphylaxis or hypersensitivity, administration of rituximab must be discontinued permanently. Patients will be asked to complete a withdrawal visit but will remain in the study (see Section 3.1.8). A schedule of assessments for the withdrawal visit is provided in Appendix 1.

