5.2.3.4 Hepatitis B Infections

Cases of hepatitis B reactivation, including those with a fatal outcome, have been reported in patients with RA, GPA, and MPA treated with rituximab.

Screening for HBsAg, HBcAb, hepatitis C serology, and HBV DNA must be performed in all patients before initiation of treatment with rituximab. Patients with positive hepatitis serology will be excluded from the study. Any patient who experiences active hepatitis B disease during the study will be immediately withdrawn from rituximab study therapy and will be followed until the common closeout date or, if required, for longer in extended follow-up (see Section 3.1.4).

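### Section 4.3.4 withdraws children with an absolute contraindication from the study and makes follow-up optional; for two overlapping safety events, Section 5.2.3 stops only rituximab and keeps them in follow-up

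*Protocol*

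**What the plan says.** Protocol Section 4.3.4 sets safety criteria to be reviewed before each infusion after the first, so it covers induction infusions 2 to 4 as well as later courses. Its absolute contraindications include "An infusion reaction which necessitated complete discontinuation of the study infusions" and "Emergent primary or secondary immunodeficiency recognized during the study period, including new HIV infection, de novo hepatitis B". The consequence is the same for every item: patients with "absolute contraindications to receipt of study infusions with rituximab will be withdrawn from the study and should be encouraged to enter Follow Up".

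Other sections give a different consequence:

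- Section 5.2.3.1 stops rituximab permanently after anaphylaxis or serious hypersensitivity, then says: "Patients will be asked to complete a withdrawal visit but will remain in the study", with a reference to Section 3.1.8.
- Section 5.2.3.4 says that a patient with active hepatitis B "will be immediately withdrawn from rituximab study therapy and will be followed until the common closeout date", or longer in extended follow-up if needed.
- Section 3.1.8, on patients taken off study drug by the investigator: "They will continue to be followed until the common closeout date".
- Section 4.6.2, where the reason for stopping the drug is an adverse event: "If possible, the patient should not be withdrawn from the study but only from study drug".

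Section 4.5.7 says of patients who leave through non-compliance or withdrawn consent that they "will be asked to return to the clinic to attend an early withdrawal visit and will be encouraged to enter follow up". Section 4.6.3 says that patients who leave the study are not replaced.

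**The concern.** The contraindications themselves are reasonable. The difficulty is the disposition attached to them. Section 4.3.4 gives safety stops nearly the wording that Section 4.5.7 keeps for families who leave the study, and so makes follow-up a matter of encouragement where other sections make it the rule.

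Adverse events are a primary outcome. Section 5.3.1 has all adverse events reported to the common closeout date. Once a patient has discontinued participation, Section 5.6 asks only for deaths, serious events and other events of concern believed to be related to study drug or procedures. SAP Section 5.1 ends observation time at the withdrawal date for early discontinuations. SAP outputs DS201SP and DS002SP count study discontinuation and treatment discontinuation separately, so sites relying on different sections could code the same event differently. Any loss would be selective, because it would fall on children who had just had a rituximab-relevant event.

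**Working it through.** This is mainly a comparison of texts.

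| Event | Section 4.3.4 | Section 5.2.3 |
|---|---|---|
| Infusion reaction ending treatment through anaphylaxis or serious hypersensitivity | Leaves the study; follow-up encouraged | 5.2.3.1: off rituximab, withdrawal visit, stays in the study under 3.1.8 |
| New active hepatitis B | Leaves the study; follow-up encouraged | 5.2.3.4: off rituximab, followed to common closeout or longer |

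**Extent of the overlap.** The events are not worded identically. Section 5.2.3.1 ties continued participation to anaphylaxis and hypersensitivity, a subset of the reactions that can end infusions. Section 5.2.3.4 speaks of active hepatitis B disease, while 4.3.4 speaks of de novo hepatitis B. The conflict is confined to children who meet both descriptions. For them, both rules are mandatory and they cannot both be followed.

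**Which section is out of line.** Sections 3.1.7 and 3.1.8 separate leaving the study from stopping the drug, and the two paragraphs of 4.5.7 do the same. Section 4.3.4 itself bars further courses after a malignancy without saying that the child leaves the study. Sections 5.2.3.5 (PML) and 5.2.3.8 (severe skin reactions) likewise stop only the drug. Section 4.3.4 is the exception.

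**Size per child.** The plan gives no figure to reproduce. The inputs are 25 patients (Protocol Section 6.1) and the Month 18 visit at Day 545 (Appendix 1).

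- Share of the sample: 1/25 = 4%.
- Total observation to Day 545: 25 × 545/365.25 = 37.30 patient-years.
- One child lost after the Day 1 infusion: (545 − 1)/365.25 = 1.49 patient-years; 1.489/37.30 = 4.0%.
- One child lost at Month 6 (Day 180): (545 − 180)/365.25 = 1.00 patient-years; 0.999/37.30 = 2.7%.

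These are upper limits for a child leaving at that time, because they assume no follow-up at all.

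**Number of children.** The documents do not support a good estimate. In adults with RA, 16 of 3194 (0.5%) had a serious infusion reaction (Section 1.2.2); 25 × 0.00501 = 0.13 children if that rate carried over, which is an assumption. In RAVE, the same disease in adults, no serious infusion reactions were reported (Section 1.2.1). No rate is given for hepatitis B, and Section 4.1.2 excludes patients with positive hepatitis B tests at screening.

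**The case against.** The best defence is that 4.3.4 is loosely worded. Its sentence sends these children to Follow Up, capitalised, and the Follow-Up Phase is part of the study. Sections 4.3.2.1.5 and 4.4.4 name 5.2.3 as the place for guidance on treatment discontinuation, and there the right disposition is given. Section 4.6.2 also lets the investigator or sponsor withdraw a patient from the study for an adverse event, so safety-based study withdrawal is not peculiar to 4.3.4.

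Part of this stands. The intent may well have been withdrawal from treatment. But 4.6.2 is discretionary and 4.3.4 is not, and no text says that 5.2.3 overrides 4.3.4. A child who has been withdrawn and encouraged to return is not in the same position as one who remains in the study.

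A reader might infer three stronger claims, and the documents support none of them.

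- *That 4.3.4 ends adverse-event and B-cell follow-up.* It weakens follow-up; the same sentence encourages it, and 5.3.1 does not expressly limit its reporting period to children still in the study.
- *That these children drop out of the safety results.* They stay in the safety population (SAP Section 3.1.1), adverse-event percentages use the number of patients in that population (AE001SP), and events before withdrawal count. The study end date in SAP 5.1 defines duration of observation, not the adverse-event window.
- *That about two children would be lost.* This would take the 8.1% of rituximab patients in RAVE with adverse events leading to permanent discontinuation: 25 × 0.081 = 2.0. That rate covers all such events, not those listed in 4.3.4, so it does not measure this problem.

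**Conclusion.** The point holds as a conflict between operative rules. For a child with permanent discontinuation for anaphylaxis or serious hypersensitivity, or with new active hepatitis B, 4.3.4 requires study withdrawal with optional follow-up, while 5.2.3.1 or 5.2.3.4 requires that follow-up continue. It should be corrected, because a site acting on 4.3.4 in good faith could lose later safety data selectively.

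The numerical effect is probably small: 4% of the planned sample per child and at most 1.49 of 37.3 patient-years to Day 545. That maximum assumes withdrawal right after the first infusion, a family that declines follow-up, and 25 patients otherwise observed to Day 545. The reason to act is which children could be lost, not how many.

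**What to change.** In Section 4.3.4, replace the consequence quoted above (study withdrawal plus encouragement to enter follow-up) with: *will be permanently withdrawn from rituximab study treatment, will complete a withdrawal visit, and will remain in the study for follow-up (Section 3.1.8)*.

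Leave the list of contraindications and the malignancy paragraph as they are. Add nothing on immunoglobulins, on precedence over 5.2.3, or on infection windows. An immunoglobulin rule would be a separate clinical decision and could narrow the immunodeficiency stop. Counting the 4-week and 2-week infection exclusions in 4.1.2 back from the next infusion would collide with the 14-day maximum delay in 5.2.3.3 and could cost children induction doses.

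The cost is a one-sentence amendment with IRB/EC approval and, where locally required, regulatory approval. No safety stop is loosened and no visit type, test or patient is added; the affected children follow the existing schedule. If follow-up has already closed, the sponsor can instead check whether any child left follow-up under 4.3.4 and report it.
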